## Protocol Summary/Submission Application

excitatory pathways in the brainstem and spinal cord (10). PSH is characterized by a constellation of symptoms such as tachycardia, tachypnea, hypertension, hyperthermia, rigidity, tremors, sweating, and pupillary dilation as a result of sympathetic hyperactivity due to the brain injury (1,5,7,8). Research on PSH has been hampered by lack of a uniform definition and use of various terms such as neurostorming, dysautonomia. Consensus diagnostic criteria and a scoring algorithm (CFS) were developed in 2014 (1) (Table 1a,1b). PSH increases the risk for secondary brain injury and is associated with worse functional outcomes, longer hospitalization and higher healthcare costs (2,3,7,11). Appropriate treatment of PSH is important for patient comfort and to prevent secondary brain damage (12,13). Currently, PSH is treated using a combination of multiple neurotropic medications (narcotics, benzodiazepines, sympatholytics, gabapentin, muscle relaxants etc.) that can result in complications due to their side effects such as excessive sedation, respiratory depression, drug dependence, and constipation. Some of these medications necessitate longer ICU stays due to their CNS depressant effects thus potentially increasing healthcare costs (3). There has been very little research into novel ways of treating PSH other than the use of various neurotropic medications (14,15).

**Measurement of autonomic function – HRV and Pupillometry** Autonomic function can be evaluated clinically and is most commonly measured using heart rate variability (HRV) (16). Established standards for measurement of HRV are available (17). HRV has been studied in various disease states in the intensive care environment such as post-acute MI, sepsis, multi-organ dysfunction, brain injury, and brain death (18,19). HRV is decreased or lost in severe disease and has been shown to be associated with increased mortality in the ICU (18,19). Higher sympathetic activity in severe disease states is associated with decreased HRV (18). HRV was shown to be significantly different between children and adults with ASBI and controls (20,21). Similarly, pupillary reactivity is also under autonomic control. Recently, pupillometry has also been used to measure autonomic activity. A pupillometer quantitatively measures pupil size (size, minimum size with light stimulus, % change in pupil size) and reactivity (constriction velocity, max constriction velocity, latency, dilation velocity) that can be compared to established norms and trended over time (22,23). These parameters have been shown to reflect

**Table 1a Clinical Feature Scale (CFS) – used for scoring**

*Clinical Feature Scale (CFS)*

	0	1	2	3	Score
Heart rate	<100	100–119	120–139	≥ 140	
Respiratory rate	< 18	18–23	24–29	≥ 30	
Systolic blood pressure	< 140	140–159	160–179	≥ 180	
Temperature	<37	37–37.9	38–38.9	≥ 39.0	
Sweating	Nil	Mild	Moderate	Severe	
Posturing during episodes	Nil	Mild	Moderate	Severe	
			CFS subtotal		
			Nil	0	
Severity of clinical features			Mild	1–6	
			Moderate	7–12	
			Severe	≥ 13	

**Table 2 PSH scoring modified for pediatric population**

## Protocol Summary/Submission Application

	0	1	2	3
Heart rate	1-4 years: <110 5-15 years: <100	1-4 years: 110-124 5-15 years: 100-119	1-4 years: 125-139 5-15 years: 120-139	1-4 years: ≥140 5-15 years: ≥140
Respiratory rate	1-4 years: <30 5-15 years: <25	1-4 years: 30-34 5-15 years: 25-29	1-4 years: 35-39 5-15 years: 30-34	1-4 years: ≥40 5-15 years: ≥35
Systolic blood pressure	1-4 years: <100 5-15 years: <120	1-4 years: 100-109 5-15 years: 120-129	1-4 years: 110-119 5-15 years: 130-139	1-4 years: ≥120 5-15 years: ≥140
Diastolic blood pressure	1-4 years: <65 5-15 years: <75	1-4 years: 65-72 5-15 years: 75-82	1-4 years: 73-79 5-15 years: 83-89	1-4 years: ≥80 5-15 years: ≥90
Temperature	<37°C	37-37.9°C	38-38.9°C	≥39°C
Sweating	Normal	Increased sweating	Localized diaphoresis	Generalized diaphoresis
Muscle tone increase	Absent	Mild increase	Neat increase	Generalized spasticity or opisthotonus

sympathetic (dilation velocity) and parasympathetic system (% change in pupil size, latency, constriction velocity) activity and sympatho-parasympathetic balance (baseline pupil size) (24). PSH, as the name implies, is associated with uncontrolled paroxysms of sympathetic activity that results in pupillary dilation among other symptoms. It is conceivable that an increase in parasympathetic activity would alter these parameters that could be compared using the patient as his/her own control

**PENFS device – description, mechanism of action, and applications** The PENFS (auricular

neurostimulator) device is a novel, non-pharmacological therapy that has been effectively used for various conditions such as functional abdominal pain, chronic pain, and narcotic withdrawal (25-27). Recent data from CW also demonstrates efficacy in a pilot study for children with cyclic vomiting syndrome, with improvement in episode severity and frequency lasting an average 5 months (unpublished data). Cyclic vomiting syndrome (CVS) is a disorder of autonomic imbalance manifested by severe sympathetic hyperactivity. Symptoms of nausea/vomiting, pallor, diaphoresis, and tachycardia are similar to PSH. Many of the symptoms of narcotic withdrawal are also very similar to those of PSH including tachycardia, tachypnea, hypertension, fever, tremors, sweating (28). Clonidine, an alpha-2 agonist with sympatholytic properties is commonly used as an adjunct in the treatment of narcotic withdrawal syndrome (29). Clonidine is also one of the first-line medications used for treatment of PSH (12,13). Thus, it is plausible that PENFS could be effective in treatment of PSH.

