## Protocol Summary/Submission Application

One of the advantages of PENFS in the treatment of PSH is that it is continuously active while it is worn thus providing symptomatic treatment throughout that period. This could help prevent or ameliorate the paroxysmal symptoms classically seen in PSH and thus reduce the need for rescue medications. The device also has been shown to have a relatively rapid onset of action. A recent study showed that the onset of action was rapid with 63% reduction in narcotic withdrawal score within 20 minutes of activation of the device and 85% reduction within 60 minutes (26). Thus, PENFS could offer a non-pharmacological tool for managing PSH, helping to decrease the need for maintenance and rescue medications and thus limiting the side effects of some of these medications. Decreased need for neurosedative medications could further decrease the length of ICU stay for these patients thus decreasing healthcare costs. The device is also well-tolerated without any serious adverse effects (25).

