### **E. Design and methods (including experimental design, technical details and laboratory methodology):**

#### **Design & Methods**

In this prospective unblinded pilot study we will enroll eligible patients until 20 parent/child dyads complete the study. It is expected many of the consented patients will not meet the eligibility criteria of CFS score > 6 (moderate severity of PSH). Those children will be considered Screen Failures and their parents/LAR told they are ineligible to continue in the study. Children admitted to the PICU at CW aged 2-17 years with ASBI and symptoms of PSH with a CFS score > 6 (moderate severity of PSH) will be eligible for inclusion. Exclusion criteria include age < 2 years (small ears thus less surface area to apply the leads), ear deformity or severe dermatitis of ear lobes, intractable seizures, heart block, patients with other implantable devices (cardiac pacemaker, vagal nerve stimulator, etc.) or known pregnancy.

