### **Aim 3b: Evaluate feasibility of measuring PENFS effectiveness in treating PSH by a decrease in medication use**

**Methods:** The maintenance medications and the number of doses and type of rescue medications administered will be collected for every 24 hours (0-24h, 25-48h, 49-72h, 73-96h, 97-120h, 121-144h, 145-168h, 169- 192h) for the enrolled patients. These will be compared to a historical cohort of PSH patients. The historical cohort will consist of PSH patients (2-17 years old) identified using the ICU Neurology administrative dataset from January 2018 – August 2021. This dataset will be used to identify ASBI patients who likely developed PSH. Eligible patients with PSH will be identified and relevant data collected by individual chart review. During this period all the PSH patients were followed by ICU Neurology thus ensuring a uniform approach to their treatment. We have also developed a practice guideline for treatment of PSH that will ensure uniform treatment of these patients during the study period. Similar to Aim 2a, we will examine the need for additional maintenance medications or change in frequency of rescue medications with discontinuation of the device. We hypothesize that, with discontinuation of the device, the patients may experience worse PSH symptoms as demonstrated by increasing CFS score and need for additional maintenance and/or rescue medications.

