## Protocol Summary/Submission Application

complete the study. If the patient does meet CFS scoring criteria for study enrollment, we will collect the CFS score for a 12-hour period before placement of the device followed by every 12 hours while the device is in place and for an additional 72 hours after removal of the device.

**Data collection & Management:** We will collect demographics, cause of ASBI, imaging findings, sedative, pain and other neurotropic medications, and maintenance and rescue medications for PSH including their number and doses for every 24-hour period from placement of the device. We will also collect all the HRV and pupillometry parameters for the 12-hour period before and after placement of the device. For the historical cohort, we will collect demographics, cause of ASBI, imaging findings, maintenance and rescue medications used in each 24 hour period for the first 120 hours and then additional 72 hours from the time of meeting CFS score > 6 criteria. . The REDCap database for this study will be developed and managed by Quantitative Health Sciences on MCW-secure servers

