**I. If children are capable of providing assent, are you planning to obtain assent from the children?**

Yes  No  **N/A – none are capable**

**If YES, describe the proposed process for obtaining assent, including who will be involved and the setting and circumstances under which it will be sought:**

**If NO, a waiver of assent is being requested** (complete IRB – **Request form for Alteration or Waiver of Assent, Consent, Parental Permission** found in IRBNet under Forms and Templates).

We are requesting a Waiver of Assent (see uploaded form) for all children due to the child’s diminished cognitive functioning. Given the inclusion criteria of nature of brain injury causing subject to meet study criteria and associated sedation necessary as standard of care for these patients, we do not anticipate that any of subjects enrolled in study will be conscious enough to comprehend, process and understand the study, so we request a waiver of assent for all subjects who will be approached for study.

If child has already completed study before achieving the age of majority, we request a waiver of consent and HIPAA authorization for continued use of their data on reaching the age of majority.

A waiver of consent/ assent is also being requested for the historical controls.

**J. If assent will be obtained, describe the process and select how assent will be documented. Include in the submission package proposed assent forms or child information sheet, if any.**

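### The device is cited as relieving narcotic withdrawal, which shares five of the six CFS items with PSH; the plan neither records withdrawal nor separates it, so CFS changes at placement and removal may partly reflect it

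*Combined protocol and SAP*

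**What the plan says.** All references are to the combined protocol and SAP.

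- **Device and withdrawal (D. Background).** The device "has been effectively used for various conditions such as functional abdominal pain, chronic pain, and narcotic withdrawal". The section then says: "Many of the symptoms of narcotic withdrawal are also very similar to those of PSH including tachycardia, tachypnea, hypertension, fever, tremors, sweating". A cited study is reported to show a "63% reduction in narcotic withdrawal score within 20 minutes of activation of the device and 85% reduction within 60 minutes".
- **Score (Tables 1a and 2; Aim 2a Methods).** The CFS items are heart rate, respiratory rate, systolic blood pressure, temperature, sweating, and "Posturing during episodes" (muscle tone in the pediatric table, with the diastolic row not scored). Each item runs from 0 to 3, and each score covers the preceding 12 hours.
- **Entry (Design & Methods; Eligibility Criteria).** A child needs acute severe brain injury, a clinical picture of PSH and a CFS above 6. Beyond age, the ear conditions and the parent's age, the exclusions are "intractable seizures, heart block, patients with other implantable devices (cardiac pacemaker, vagal nerve stimulator, etc.) or known pregnancy". None concerns opioid or sedative withdrawal.
- **Drug exposure.** Morphine and benzodiazepines are rescue drugs, the background names drug dependence as a complication of PSH treatment, and the assent section refers to "associated sedation necessary as standard of care for these patients".
- **Drug data.** Data collection & Management lists sedative, pain and neurotropic drugs, then maintenance and rescue drugs with number and doses "for every 24-hour period from placement of the device". Table 3 adds maintenance and rescue drugs for the 12 hours before placement.
- **Interpretation.** Aim 2b evaluates effectiveness by within-patient CFS change. Aim 3b expects that after removal "the patients may experience worse PSH symptoms as demonstrated by increasing CFS score and need for additional maintenance and/or rescue medications". The only confounder named for the CFS trend is new maintenance medication.

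**The concern.** The protocol uses the resemblance between withdrawal and PSH to argue that the device is plausible for PSH, but does not treat the same resemblance as a rival explanation for its own outcome. If some children are in narcotic withdrawal when the device goes on, a device that relieves withdrawal will lower their CFS whatever it does to PSH. If a child is in withdrawal when the device comes off at 120 hours, the score may rise, and Aim 3b would read the rise as returning PSH. A fall followed by a rise would look like two confirmations of one effect, although both could share this other source. With no concurrent control, nothing else in the design tells the two apart. At stake is the interpretation of Aim 2b and of the discontinuation reading in Aim 3b.

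**Working it through.** The plan states no figure for this point. The sample of 20 is a convenience sample, so there is nothing to reproduce.

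**Step 1. Overlap of signs and items.** Tachycardia, tachypnea, hypertension, fever and sweating map to heart rate, respiratory rate, systolic pressure, temperature and sweating. Tremor has no CFS item, and posturing (or muscle tone) has no match on the list. The overlap is 5 of 6 items, or 5 × 3 = 15 of 6 × 3 = 18 points (83%). This holds for Table 1a and for Table 2 as scored. Three shared items at their maximum give 3 × 3 = 9, above the entry cut of 6 with posturing at 0.

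**Step 2. Timing.** The cited relief occurs at 20 to 60 minutes, early in the first 12-hour window after placement. If it lasted, it would cover at least 11 of the 12 hours.

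**Step 3. What the record would show.** Rescue opioids and benzodiazepines are captured for the 12 hours before placement. A wean completed earlier is not. The wording leaves open whether sedative and pain drugs outside the maintenance and rescue lists are recorded before placement at all. No withdrawal diagnosis or score appears in Table 3, and the analysis section uses none of the drug data to separate withdrawal from PSH.

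**Step 4. Illustrative size.** The assumptions below are not in the documents unless noted:

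- 20 children (documents), baseline CFS 10, SD of change 3 or 4
- no device effect on PSH and no natural decline
- each child independently in withdrawal with probability *p*
- in affected children, a fraction *f* of the shared-item points is due to withdrawal
- those points fall by *r* = 0.63 or 0.85 (the cited withdrawal-score reductions, carried over to the CFS)

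Mean CFS fall = *p* × 10 × (15/18) × *f* × *r*. For *p* = 0.20 and *f* = 0.5, this is 0.20 × 8.33 × 0.5 × 0.63 = 0.53, or 0.71 with *r* = 0.85.

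The chance of a significant fall (one-sample t-test on the change, two-sided 5%, falls only) was simulated with the shift applied to affected children only:

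| Share affected | Fraction *f* | Mean fall (points) | Significant fall |
|---|---|---|---|
| 0% | – | 0 | about 2.5% |
| 20% | 1/4 | 0.26–0.35 | 5–7% |
| 20% | 1/2 | 0.53–0.71 | 8–14% |
| 20% | all | 1.05–1.42 | 16–28% |
| 40% | 1/4 | 0.53–0.71 | 8–16% |
| 40% | 1/2 | 1.05–1.42 | 18–41% |
| 40% | all | 2.10–2.83 | 47–75% |

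Repeat runs differ by up to about one percentage point.

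**The case against.** The case against has several parts, and much of it stands as a limit on the claim.

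- **Entry is not by score alone.** ICU Neurology and Critical Care must first judge that the child shows PSH. This lowers the risk. It does not remove it: no written rule separates withdrawal from PSH, and one child can have both. The protocol also cites a Table 1b, which is not in the text available here, so its content cannot be judged; Aim 1 Methods base eligibility on Table 1a.
- **Drug use before placement is not unrecorded.** A reader might infer from Data collection & Management that collection starts only at placement. Table 3 shows otherwise for maintenance and rescue drugs in the prior 12 hours. The gap is earlier weaning and the absence of any use of the record.
- **No significance test or success rule is planned for the CFS change.** The analysis section gives a Spearman correlation for Hypotheses 2a and 2b, and mixed models to describe change over time. The percentages above therefore show scale and are not error rates of this trial.
- **The top row for each share is extreme.** Attributing all shared-item points to withdrawal leaves affected children almost without PSH on those items, which sits badly with coexistence. The quarter and half rows fit that picture better.
- **Only narcotic withdrawal is cited as responding to the device.** The documents do not support extending the mechanism to benzodiazepine withdrawal.
- **This is a feasibility pilot, stated not to be powered for efficacy.** That softens the consequence, but Aim 2b is still framed as an evaluation of effectiveness.

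**Conclusion.** The point holds as a limit on attribution. The overlap (5 of 6 items, 15 of 18 points), the cited withdrawal effect, and the absence of any exclusion, diagnosis, score or analysis for withdrawal all stand in the documents. A CFS fall at placement, or a rise after removal, may partly reflect narcotic withdrawal and cannot be credited to PSH alone.

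A reader might go further and infer that a positive result would be withdrawal relief, or that the trial has a large false-positive rate. The documents support neither: they give no prevalence of withdrawal, no share of CFS points due to it, and no planned test of the CFS change. With 20% affected, the illustrative figures run from 5–7% to 16–28% depending on one unknown fraction, and they assume that the cited relief carries over to a 12-hour score. This is a cheap improvement to interpretation, not a flaw that invalidates the pilot.

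**What to change.** 1. In Data collection & Management and Table 3, extend abstraction of opioid and sedative doses to a fixed look-back before placement, with its length stated before analysis. Record any diagnosis of withdrawal made by the clinical team.
2. Define a baseline flag from pre-placement data only: an opioid infusion or scheduled opioid course reduced or stopped within the look-back, or withdrawal recorded.
3. Under Hypothesis 2b, report the CFS change at placement for all children and again without flagged children, as a pre-specified sensitivity analysis.
4. For the removal contrast (Aim 2b and Aim 3b Methods), describe opioid reductions during wear and name withdrawal as an alternative explanation beside maintenance medication. Do not drop CFS windows because of reductions after placement: lower drug use is the hypothesised device effect, so that would select on response.

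None of this changes treatment or eligibility. The cost is some extra chart abstraction, and the unflagged set will be smaller and its estimates less precise.

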**Figure 1. PENFS device**

The PENFS device is applied over the external ear (Fig.1) and is continuously worn for 120 hours at a time. The electrical current stimulates the auricular branch of the vagus nerve (ABVN) and auricular branches of cranial nerves V, VII and IX. The nerves project to the various parts of the brain, including the brainstem nucleus tractus solitarius. fMRI scans in healthy human volunteers have shown significant activation of the central vagal projections by stimulating ABVN (30). Sympathoinhibition has been shown to be one of the primary mechanisms of actions of the device in the various conditions for which it is used (31-33). The study by Mahadi et al., showed that electrical stimulation of the tragus in rats resulted in central sympathoinhibition by up to 36% within 5 minutes of stimulation (31). This central sympathoinhibition by the PENFS device could improve the symptoms of PSH.

## Protocol Summary/Submission Application

One of the advantages of PENFS in the treatment of PSH is that it is continuously active while it is worn thus providing symptomatic treatment throughout that period. This could help prevent or ameliorate the paroxysmal symptoms classically seen in PSH and thus reduce the need for rescue medications. The device also has been shown to have a relatively rapid onset of action. A recent study showed that the onset of action was rapid with 63% reduction in narcotic withdrawal score within 20 minutes of activation of the device and 85% reduction within 60 minutes (26). Thus, PENFS could offer a non-pharmacological tool for managing PSH, helping to decrease the need for maintenance and rescue medications and thus limiting the side effects of some of these medications. Decreased need for neurosedative medications could further decrease the length of ICU stay for these patients thus decreasing healthcare costs. The device is also well-tolerated without any serious adverse effects (25).

### **Innovation:**

The treatment of PSH has been limited to various combinations of neurotropic medications. We explore the novel use of an auricular neurostimulator (PENFS) device for PSH treatment. We hypothesize that the PENFS device, by stimulating the parasympathetic AVBN will inhibit the sympathetic hyperactivity due to PSH. If this approach proves to be efficacious, it will help to decrease the need for neurotropic medications thus decreasing some of the serious adverse effects of these medications (drug dependence, acute cardiorespiratory compromise due to neurodepressant effects, constipation and feeding intolerance due to bowel dysmotility). The PENFS device is worn continuously for 120 hours thus providing continuous treatment of PSH symptoms which would potentially decrease the need for rescue medications. Limiting the need for neurodepressant medications would reduce the need for close monitoring in the ICU resulting in decreased healthcare costs. The use of objective measures of autonomic function - HRV and pupillometry – is also a novel way of evaluating response to treatment using the PENFS device. Further, the application of the CFS score in pediatrics will potentially provide a simple, instantaneous mode of tracking symptoms severity and response to treatment.

